**In-depth interviews**

- *Sixty-six IDIs with caregivers, after initial study product use and after prolonged use:*  
The goals of the IDIs are to understand the experiences of the caregivers when administering study product to their child, how they perceive the value of the product, the potential advantages and

disadvantages of study product, and the factors relating to uptake. Topics explored in the IDIs will include:

- Perceived palatability of solutions by children.
- Ease of use, including how easy it was to understand use instructions and administer to the child.
- Behavioral intention to use.
- Perceived acceptability of study product by caregivers of children.

Please see Appendix 2 for IDI guide and DO checklist.

#### *Blood Specimen Collection and Processing*

Between 1 and 1.5 ml venous blood will be collected from each child twice—at enrollment and at the post-dosing visit, 15 days after onset of the intervention. A trained phlebotomist will perform venipuncture using a technique appropriate for children who are younger than 2 years old, and a small drop of blood will be blotted from the insertion site and dried on filter paper. Blood samples will be centrifuged into plasma and/or serum within 30 minutes of collection and stored in cryo tubes at less than  $-20^{\circ}\text{C}$  until they can be analyzed. Commercial enzyme-linked immunosorbent assays (ELISA) and a Quansys Biosciences Q-Plex™ panel will be used to quantify plasma/serum micronutrients, EED markers (intestinal fatty acid-binding protein [I-FABP], soluble CD14 [sCD14], glucagon-like peptide 2 [GLP-2], insulin-like growth factor 1 [IGF-1], and fibroblast growth factor 21 [FGF21]), and systemic inflammation (alpha-1-acid glycoprotein [AGP] and C-reactive protein [CRP]). Mass-spectroscopy will be used to evaluate metabolic markers from dried bloodspot (e.g., acylcarnitine profile) to ascertain whether there is a tendency for child metabolism to switch to an oxidative state when supplementing a subset of essential amino acids. Detail provided in Table 5, below.

**Table 5.** Plasma/serum biomarkers assessed in SAFE at enrollment and post-dosing visit.

Biomarker	Assay name	Company	μl of plasma required (per well)
I-FABP	Human I-FABP ELISA	Hycult	25
GLP-2	GLP-2 ELISA Kit	ALPCO	25
IGF-1	Human IGF-I Quantikine ELISA Kit	R&D Systems	20
sCD14	Human CD14 Quantikine ELISA Kit	R&D Systems	10
FGF21	Human FGF-21 Quantikine ELISA Kit	R&D Systems	50
AGP	Q-Plex™ Human Micronutrient (7-Plex)	Quansys	10
CRP			
Ferritin			
sTfR			
RBP4			
Thyroglobulin			
HRP2			
Acylcarnitine	Acylcarnitine profile analysis	Mass spectrometry	40 (80 μl whole blood)
Total			320

### *Discontinuation of Study Product Use and Withdrawal From the Study*

Participants have the right to decline study procedures for any reason and at any time during the study with no penalty. If a participant decides to discontinue study procedures, including AA-ORS or placebo administration, this will be recorded as a study deviation and the reason will be clearly documented.

Participants have the right to withdraw from the study at any time and for any reason, without penalty. If a caregiver does not wish to remain in the study and/or decides to stop administering the solution altogether to his/her child, the participant can choose to withdraw consent and be withdrawn from the study. That decision will be documented, and study staff will attempt to schedule a final post-dosing IDI and medical examination as soon as possible to confirm the welfare of the child.

The principal investigator and site PI may, at their discretion, withdraw a subject from continuing in the study if it is considered to be in the participant's best interest to do so, or if the participant is not willing or able to comply with the study requirements. The reason for withdrawal will be documented. Withdrawn subjects will not be replaced in the study. The data collected before withdrawal will be analyzed.

Withdrawal from further study product administration may be at the discretion of the PI or site PI, in consultation with the study pediatrician if it is in the interest of the subject. In addition, participants will be withdrawn from further study product administration for the following reasons:

- Ineligibility (either arising during the study or retrospectively having been overlooked at enrollment).
- Significant protocol deviation.
- Significant noncompliance with the study product regimen or study requirements.
- Significant weight loss: if a child loses more than 5% of his or her body weight from that measured at enrollment, the child will be withdrawn from the study. The study team will refer the withdrawn child and caregiver to his or her primary health care provider or CGH, as appropriate.
- An AE (including intercurrent illness, diseases, or medical treatment) that requires discontinuation of study product use or results in inability to continue to comply with study procedures (Appendix 2). The study team will refer anyone that develops an acute illness during the study to his or her primary health care provider or CGH, as appropriate.

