**Stopping rule:** RAs will weigh children in the household on a weekly basis (end of weeks 1 and 2). If a child loses more than 5% of his or her body weight from that measured at enrollment, he/she will be withdrawn from the study. The study team will refer the withdrawn child and caregiver to his or her primary health care provider or CGH, as appropriate. In addition, there will be a review of the first 10 enrolled breastfeeding participants by the investigators and ISM. If two of the first 10 participants who are breastfeeding at enrollment stop breastfeeding during the 2-week course of the study, the study will halt the enrollment of children who are currently breastfeeding. If there is evidence of a negative impact on participants' breastfeeding, PATH REC will be notified.

**Unsolicited AEs** are any significant events not specified as a solicited AE by study personnel and can be reported spontaneously by the participant, observed by the study personnel during study visits, or identified during review of medical records or source documents.

Any medical condition that is present at the time that the participant is screened will be considered as baseline and not reported as an AE. However, if the study participant's condition deteriorates at any time during the study, it will be recorded as an AE.

Changes in the severity of an AE will be documented to allow an assessment of the duration of the event at each level of severity to be performed. AEs characterized as intermittent require documentation of onset and duration of each episode.

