#### *Reporting Period and Parameter*

Safety events are reported from the time of the first study product administration through completion of the study 21 days later. Specifically, solicited AEs will be collected up to 30 minutes after the first administration and on days 4, 7, 14, and 21. Both solicited and unsolicited AEs and SAEs will be assessed through 7 days after the end of the study product dosing. The final AE and SAE assessment will be done via a phone call on day 21 (or within 3 days thereafter):

1. The caregiver will be contacted via telephone and identity confirmed.
2. Study nurse will ask about any medical event that would constitute an AE or SAE since the last visit.
3. If an AE or SAE is reported, the nurse should record it on the appropriate CRF and consult the study clinician, who will notify the entities who require notification. The nurse will refer the participant for treatment, if warranted.

After recording the information, the participant will be discharged from the study.

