#### *Follow-up of Adverse Event*

All reported AEs should be followed until resolution or stabilization, or until the participant’s participation in the study ends. Participants who have an ongoing study product–related SAEs at study completion or at discontinuation from the study will be followed by the PI or his designee until the event is resolved or determined to be irreversible, chronic, or stable by the PI.

The outcome of an adverse event will be assessed as at the time of last observation as per the following categories:

- Recovered/resolved without sequelae.
- Recovered/resolved with sequelae.
- Ongoing at the end of the study.
- Death.
- Unknown. The outcome of the AE is not known.

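### The weight-loss rule sits in a list of reasons to stop product but takes the child out of the study, leaving it unclear whether adverse event follow-up continues to day 21.

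*Combined protocol and SAP*

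**What the plan says.** Section C.iii, Discontinuation of Study Product Use and Withdrawal From the Study, treats stopping product and leaving the study as separate outcomes. Its list opens with product only: "participants will be withdrawn from further study product administration for the following reasons". Under the weight-loss bullet, however, a child who loses more than 5% of body weight "from that measured at enrollment, the child will be withdrawn from the study". The stopping rule in section C.x, Definition of Adverse Event (AE), repeats this: a child with such a loss "from that measured at enrollment, he/she will be withdrawn from the study". The neighbouring bullet, on other adverse events, does not mention study withdrawal.

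The action stated for a child withdrawn for weight loss is referral to a primary provider or the county hospital. For a caregiver who withdraws consent the same section goes further: "study staff will attempt to schedule a final post-dosing IDI and medical examination as soon as possible to confirm the welfare of the child".

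On what happens next, section C.x, Follow-up of Adverse Event, says "All reported AEs should be followed until resolution or stabilization", or until the participant's "participation in the study ends". The stated exception is that ongoing product-related "SAEs at study completion or at discontinuation from the study will be followed by the PI or his designee".

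Other parts of section C.x describe the full window. Reporting Period and Parameter says "Safety events are reported from the time of the first study product administration through completion of the study 21 days later", with a final call on day 21. It also says that assessment runs for 7 days beyond the end of dosing. Adverse Events and Serious Adverse Events has the nurse monitor every participant at five time points, and solicited events are monitored for all 21 days. Section C.xi compares the arms on events within 21 days of enrollment, using Fisher's exact test.

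**The concern.** Weight loss is a solicited adverse event, and the toxicity table in Appendix 8 grades a loss of 5% to under 9% as moderate and 9% or more as severe. A rule that removes a child from the study at that point can stop observation because of a safety outcome, around the moderate threshold and before any progression to severe is seen. Later events of other types, serious events, worsening grade and duration by severity could all go under-recorded in these children.

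The child stays in the safety population, because section C.xi keeps everyone who received a dose, and no imputation is planned. A truncated child with no further recorded event therefore counts as having none. The direction of any bias depends on trigger rates and later event rates in each arm; even equal truncation can shrink a true excess on AA-ORS. The planned check for differential missingness by arm would show such a loss but could not recover the data.

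**Working it through.** **Plan's own figure.** Sampling Strategy, Table 6, gives a 95.8% chance of at least one event with 30 per arm and a true rate of 10%. Check: 1 − 0.9^30 = 0.9576, so it reproduces.

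**Inputs.** The window is 21 days (Endpoints). Weighing is at the end of weeks 1 and 2 (stopping rule), taken as days 7 and 14. There are five nurse assessments: after the first dose and on days 4, 7, 14 and 21. The enrolled arm size is 33. The 10% event rate is from Sampling Strategy. The number of triggers is not in the documents and is assumed.

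**Follow-up lost per triggered child.** The call on the trigger day is taken as done.

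| Reading | Day-7 trigger | Day-14 trigger |
|---|---|---|
| Study withdrawal ends scheduled follow-up | 21 − 7 = 14 days (67%); 2 of 5 assessments; also the day-14 weight and day-15 examination | 21 − 14 = 7 days (33%); 1 of 5 assessments; also the day-15 examination |
| Follow-up for 7 days after that child's last dose | about 7 days; 1 call | none |
| Full 21-day schedule governs | none | none |

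**Missed first event per truncated child.** Assume a constant hazard, a 21-day risk p and observation that ends on day t. The chance of missing a first event of a given type is (1 − p)^(t/21) − (1 − p).

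- p = 0.10: t = 7 gives 0.0655; t = 14 gives 0.0322.
- p = 0.30 (assumed): t = 7 gives 0.1879; t = 14 gives 0.0884.

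**Chance that an arm of 33 shows at least one event with a 10% rate.** With k day-7 triggers on the most severe reading, each contributes a third of its window: 1 − 0.9^(33 − k + k/3).

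- k = 0: 1 − 0.9^33 = 96.9%.
- k = 1: 96.7%.
- k = 3: 1 − 0.9^31 = 96.2%.
- k = 5: 95.6%.
- k = 6: 1 − 0.9^29 = 95.3%.
- k = 7: 1 − 0.9^28.33 = 94.9%.

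On the most severe reading, it therefore takes 7 day-7 triggers among 33 children (21%) to fall below 95%.

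**Effect on a between-arm difference.** Assume 3 day-7 triggers in each arm of 33 and true risks of 30% and 10%. The recorded risks are 0.30 − (3/33)(0.1879) = 0.2829 and 0.10 − (3/33)(0.0655) = 0.0940. The difference shrinks from 20.0 to 18.9 percentage points.

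**The case against.** The strongest reply is that the protocol never says collection of new events stops at withdrawal. The follow-up section concerns the course of events already reported; the schedule for finding new events is set elsewhere and runs to day 21 for all participants. The sentence on 7 days beyond the end of dosing, if applied to each child, would give an intermediate answer, though the text does not say whether it applies per child. This stands, and it is why the losses are stated as upper limits.

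A reader might infer that the protocol definitely ends adverse event collection for these children. The documents do not support that: it is the natural reading of the withdrawal and follow-up sections together, but other sections contradict it and none takes precedence. A reader might also infer that safety detection drops below the planned 95%. That would come from counting triggers on top of an arm already cut to 30, but Sampling Strategy says expected withdrawal of up to 10% is already built into the 33. If 3 of 33 children contributed nothing at all, 30 would remain and the chance would be the planned 95.8%.

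The harm is also limited by what is kept: the triggering weight loss, all data before withdrawal, and follow-up of ongoing product-related serious events. Wasted and acutely ill children are excluded at entry. Procedures or the study manual, which are not in the documents reviewed, may instruct staff on the day-21 call. None of this removes the contradiction in the protocol. The independent monitor is asked to confirm that appropriate follow-up took place, which leaves open what is appropriate for these children.

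**Conclusion.** The conflict is real and appears in two places: a reason to stop product is written as withdrawal from the study. Whether this cuts safety observation before day 21 depends on which section staff follow. The most a triggered child can lose is 14 of 21 days and 2 of 5 assessments at day 7, or 7 days and 1 assessment at day 14; the least is nothing.

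The any-event comparison is unaffected. Only later events, and the later course of existing ones, are at risk in these children. With no trigger rate in the documents, the trial-level figures rest on assumed counts and a constant hazard. Within 1 to 5 day-7 triggers per arm of 33, the detection chance stays above 95%. The effect is small unless triggers are frequent, and the severity is minor. The point is worth making because the rule can end observation in children already showing a safety signal, and the correction is cheap.

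**What to change.** In both places, the discontinuation section in C.iii and the stopping rule in C.x, make the consequence withdrawal from further study product rather than from the study, and keep the referral to care. State that, unless the caregiver withdraws consent, the child stays in the scheduled day-14 contact and weighing, the day-15 examination and the day-21 call. Allow the day-15 blood draw to be omitted if the study clinician judges it inappropriate. State that these data enter the safety analysis.

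The cost is a protocol amendment, which under the statement of compliance in section A needs sponsor agreement and documented ethics and regulatory approval. No new visits are needed, since all these contacts are already scheduled. Stopping product already ends exposure, so the child gives up no protection by staying under observation.

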### *Sampling Strategy*

Estimated sample size: We expect to enroll 132 participants, which includes 66 caregivers, and 66 children (aged 12–24 months); half of these child-caregiver pairs will be randomized to receive AA-ORS (n= 33) and half to receive placebo solution (n= 33). We anticipate that there will be a dropout rate not to exceed 10%. We have incorporated this expected withdrawal rate into the final sample size numbers.

For the primary endpoint of safety in this study, 30 subjects in each arm would result in more than 95% probability of observing at least one AE if the rate of that type of event in the subject population after being exposed to AA-ORS is 10%. To have a 95% probability of being able to detect at least one AE if the rate of that event is truly 5%, the sample size would have to be at least 60 per arm. For more

rare events, the sample size would have to be much larger. Table 6 below shows the probabilities of observing an event with various sample sizes and varying true rates of that event in the population.

**Table 6.** Probability (P) of observing none, one, or more adverse events (AEs) at different true rates of AEs in the population.

N (per arm)	Rate of AE	P of 0 AEs	P of 1+ AEs	P of 2+ AEs	P of 3+ AEs
20	0.15	3.9%	96.1%	82.4%	59.5%
	0.2	1.2%	98.8%	93.1%	79.4%
30	0.1	4.2%	95.8%	81.6%	58.9%
	0.15	0.8%	99.2%	95.2%	84.9%
40	0.1	1.5%	98.5%	92.0%	77.7%
	0.15	0.2%	99.9%	98.8%	95.1%
50	0.1	0.5%	99.5%	96.6%	88.8%
	0.15	0.03%	99.97%	99.7%	98.6%
60	0.05	4.6%	95.4%	80.8%	58.3%
	0.1	0.2%	99.8%	98.6%	94.7%

Gray highlighted cells are those with a probability of 95% or higher. Blue highlighted cells are those representing a true AE rate of 0.1 or lower.

Increasing the per-arm sample size above 30 (but < 60) does not add much in terms of increasing the probability of detecting an AE with a true rate in the population of 10%. However, 30 subjects per arm has relatively low power for an efficacy endpoint using biomarkers. For example, a sample size of 30 per arm provides approximately 80% power for a t test to detect a 376 ng/ml (21.9% reduction) difference in soluble CD14 (marker of bacterial translocation) between the arms assuming the mean sCD14 is 1,715 ng/ml in the placebo group. These calculations used data from an infant cohort in Zimbabwe (23) (SD = 520 ng/ml).

#### *Recruitment and Consent Procedures*

##### Recruitment of child and caregiver participant pairs:

Children and their caregivers potentially eligible for the study will be identified by clinic staff from the child welfare clinic (CWC), which is the outpatient department where they are administered routine child immunizations (measles and yellow fever at 9 months of age, but sometimes postponed until the second year), healthy child visits, or receive routine Vit. A supplementation (at 12 and 18 months of age). Potential participants will be screened using medical records that include child anthropometry and medical history. Height and weight will be converted into z-scores using an algorithm.

- a. Recruitment at clinic visit: During the potential participant's CWC visit, a study RA will introduce the study to the caregiver and ask if they are interested in learning more. Following a short recruitment script (Appendix 5), study staff will inform the caregivers that a research study on a product that may improve pediatric gut health will be tested. If the caregiver is interested in learning more about the study, the caregiver will be provided with a product information form and study consent form to take home and review before returning to the clinic for an enrollment visit. If the caregiver declines enrollment in the study, any medical record data collected will be discarded and shredded.
- b. Recruitment from CWC register: Study RAs will identify potentially eligible children from CGH CWC register that lists childrens' names, age, caregiver contact information, exclusive breastfeeding status, and anthropometric measurements from patients receiving immunizations in the first year of life. The hospital has approved using retrospective data from the CWC register for this pre-screening activity. The CWC register is an alternative recruitment

mechanism whereby the caregivers of children who have been seen previously for routine EPI immunizations (such as measles and yellow fever vaccine at age 9 months) will be contacted for potential interest in study participation. The RA will record information into a pre-screening log from the register for children who would currently meet age eligibility requirements, limited to CWC visit date, child age, name, and contact number. RAs will call the caregivers of prospective participants using the telephone number provided and introduce the study to the caregiver and ask if they are interested in learning more. Using a short telephone-specific recruitment script (Appendix 5), study staff will inform the caregivers that a research study on a product that may improve pediatric gut health will be tested. If the caregiver is interested in learning more about the study, they will be invited to set up a screening visit (to be conducted at the CWC) where they will be provided with a product information form and study consent form to take home and review before returning to the clinic for an enrollment visit. If the caregiver is not interested in the study during the phone call and declines to schedule a screening visit, their information in the pre-screening log will be blotted out using dark ink. If the caregiver declines enrollment in the study at the screening visit, any medical record or contact data previously collected will be shredded and discarded or blotted out, as applicable.

Following the visit, those who are still interested and eligible will be scheduled to undergo the informed consent process and enrollment visit at CGH at a time convenient to them, 1–3 weeks after the immunization or Vit. A supplementation visit, or whenever is convenient for those who had been identified from the CWC register (but did not receive immunizations or Vit. A supplementation). The delayed enrollment visit is to avoid conflating potential immunization-related AEs with those related to the study product. Caregivers will receive a reminder call from study staff the day before their scheduled enrollment visit. During the appointment reminder call, caregivers will be advised of changes that would make them ineligible (to avoid an extra trip to the hospital). These changes include diarrhea in household in past week, child acute illness, and child antibiotic treatment within the past 2 weeks. If the child is no longer eligible based on one of these changes, the enrollment visit will be postponed and rescheduled or cancelled, depending on the caregiver's preference. The caregiver will be told that they have the option to decline to participate at the time they are contacted by the study team or any time thereafter.

Children and their caregivers will be recruited as a dual enrollment participant pair. Upon their return to the facility, the RA will escort the caregiver and child to a private exam room where they will review the consent form and answer questions they may have. The RA will confirm that both the child and caregiver still meet both sets of eligibility criteria. The RA will then obtain written informed consent from willing and eligible caregivers prior to the child medical examination, blood draw, IDI, and administration of AA-ORS or placebo solution.

All participants will be informed that the study does not offer any direct benefit to them and the use of this product is currently for exploratory research purposes only. The study does not aim to assess the reliability or compare the outcomes of AA-ORS to the standard of care. The information participants will provide throughout this study is not considered sensitive and will not pose any significant risk to them personally. Participants have the option to decline being interviewed for the study without any negative consequences.

Once informed consent is obtained, participants will be assigned an identification number that will be used to identify the paper forms, solution consumption data, and blood specimens collected from that patient during the study. No personal identifying information will be recorded on any of the data collection tools.

